7.2 Subgroup Definitions

No specific subgroups are designated.

8 Definition of Time Points and Analysis Variables

8.1 Definition of Time Points

Analyses of endpoints will be performed based on evaluations obtained on days 0, 28±2, 56±4 and 28±4 days after discontinuation of study treatment.

Baseline will be defined as the value collected at the Baseline Visit. Study day 1 is, subsequently defined as the day after the Baseline Visit.

The Treatment Day of an event/assessment will be calculated relative to the First Study Treatment Administration as specified on the eCRF page ‘Study Drug Dosing Dates’.

The Treatment day of events/assessments occurring before the First Study Treatment Administration was calculated as:

- Treatment Day = (Date of assessment/event - Date of First Study Treatment Administration).

For events/assessments occurring on or after First Study Treatment Administration, Treatment Day will be calculated as:

- Treatment Day = (Date of assessment/event - Date of First Study Treatment Administration) + 1.

Visits will be analysed as they were collected. Unscheduled visits during study treatment will be considered for imputation purposes only (Last-observation carried forward). In case of unscheduled visits occurring before first treatment, the latest non-missing assessment will be considered as baseline value, respectively.

Conformance with the visit schedule will be evaluated during the BDRM. In case of substantial deviations from visit schedule, a supportive analysis will be considered to investigate influence of these deviations on primary as well as secondary endpoints and documented in BDRM minutes.

Study completers will be defined as patients, who answered the question “Did the patient complete the study” on the eCRF page ‘End of Study’ as YES.

Table 2: Study Visits

Scheduled Visit	Scheduled Visit Label	Scheduled Study Day	Visit Window
Baseline Visit Day 0	Baseline	0	Study day = 0
Week 4	Week 4	28	Study day in [26 – 30]
Week 8	Week 8	56	Study day in [52 – 60]
Follow-up Visit Week 12	Week 12	84	Difference Date Week 12 – Date of Last Study intake in [24 – 32]
Documented unscheduled Visits will be labeled as “Unscheduled Visit 1”, “Unscheduled Visit 2”.....			
For Visit Window Week 12, Date of Last Study Intake as specified on eCRF Page “Study Drug Dosing Dates”			

8.2 Analysis Variables

This chapter describes all endpoints which will be summarized as described in section 10.

8.2.1 Disposition parameters

Disposition parameters are recorded on the eCRF Page 'End of Study'.

Study discontinuations will be defined only for patients in the Enrolled Set. A patient discontinued the study prematurely, if the question 'Did the patient complete the study' was answered as 'No'.

Primary Reason for Study Discontinuation is documented on the eCRF Page 'End of Study' in categories 'Adverse Event', 'Lost to Follow-Up', 'Decision unrelated to an Adverse Event', 'Non-Compliance', 'Study terminated by the sponsor', 'Study terminated by the investigator', 'Other'.

If the study day of discontinuation/study completion as documented on the eCRF page is below 52 days, discontinuation will be considered as 'During Treatment Period', otherwise it will be considered as 'During Follow-Up Period'.

If the eCRF question 'Was the emergency envelope opened during the study?' was answered 'Yes' the patient will be considered as unmasked.

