3.1.3 Route and method of administration

Administration route and dose regimen for Groups 1 and 2 will be:

Group 1: *rhNGF 20 µg/mL*: One drop (40 µL) corresponding to 0.80 µg of rhNGF will be instilled into each eye six times daily, for a total daily dose of 9.60 µg (both eyes), for 56 consecutive days. Total dose will be 537.6 µg/56 days.

Group 2: *vehicle*: One drop of vehicle (40 µL) will be instilled into each eye six times daily, for 56 consecutive days.

For both groups 1 and 2, the patients will self-administer the drops at home. In all patients, both eyes will be treated as specified above, whereas only the “worse eye” (i.e. the eye with the more severe dry eye) will be the study eye. The Investigator will check that all patients take the IMP appropriately verifying the diary and the used medication returned.

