Week 4 Visit	Day 28±2	
The following procedures will be performed (order below is not mandatory):
 
 ➤ Assessment of compliance to treatment (from patient diary and IMP reconciliation from returned weekly boxes) ➤ Current medical conditions ➤ Concomitant medications ➤ AE monitoring ➤ Ocular examination of both eyes: 
 1. Assessment by SANDE questionnaire 2. Assessment of best corrected distance visual acuity (BCDVA) 3. Slit-lamp examination (SLE) to assess the Eyelid - Meibomian glands, Eyelid – Erythema, Eyelid - Edema Lashes, Conjunctiva Erythema, Lens, Iris, Anterior Chamber 4. External Ocular Examination 5. Tear Film Break-up Time (TFBUT) 6. Ocular surface staining (NEI score - Fluorescein and Lissamine green) ➤ Study Drug Dispensation 
The Investigator will deliver to the patients their monthly box containing the study drug for the following 4 weeks together with an adequate number of adapter and pipettes.
 
After discharge the patients will continue the therapy as per instructions and will self-administer at home the subsequent doses from the evening of Day 28±2 to the evening of Day 56±4. Patients will return to the clinical site on Day56 ± 4 (Week 8 Visit).
 
The patients will be instructed to enter time of self-administration, AE occurrence, and concomitant medication intake into the diary, and to return the refrigerated box on the Week 8 visit.

At home	Days 28±2 – 56±4	
 ➤ Self-administration at home of the IMP, six times daily for every 2 h (diary) ➤ Recording any new or changes concomitant medications (diary) ➤ Recording any unusual medical conditions - AE monitoring (diary) 
Data will be recorded by the patient on the patient's diary.

	Day	Procedures/Assessments

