- An AE leading to study discontinuation is defined as an AE where in the eCRF section ‘Action regarding Patient’ the box ‘Patient Withdrawn’ is ticked (this should match with the primary reason for early withdrawal of ‘Adverse Event’ on the End of Study eCRF page).
- An AE is classified as ‘Related’ to Study Treatment if the relationship to study medication recorded as ‘Possible’ or ‘Probable’ or ‘Highly Probably’. An AE will be classified as unrelated to study medication if the relationship to study medication was recorded as ‘None’ or ‘Unlikely’. AEs with missing relationship to study treatment will be counted as ‘Related’ to Study Treatment.
- A Fatal AE is defined as an AE where the outcome is recorded as ‘Fatal’.

These definitions will apply accordingly also for the subsequent sub-classes of AEs.

Non Treatment-emergent adverse events (Non-TEAEs)

A Non-TEAE is defined as any AE, which started before the first administration of study treatment. They are identified by the ticked box ‘Before Treatment Period’ in the eCRF Section ‘Did the event occurred.’.

According to the study protocol, both eyes of a patient should be treated. However, there might be the situation, that one eye will not be treated (which will, in fact, be a protocol deviation). For such cases, all ocular events occurring in an eye, which were not treated as indicated on eCRF page 'Study Eye', will also be considered as Non-TEAE irrespective of the timepoint of occurrence.

Treatment-emergent adverse events (TEAEs)

A treatment-emergent adverse event is defined as an AE that started on or after the date of the First Study Treatment Administration. An TEAE will be identified, if

- The eCRF question 'Did the event occurred:' was answered either with 'During Treatment period' or 'During Follow-Up Period'

and

- In case of an ocular event: the affected eye was treated as indicated on the eCRF page 'Study Eye'.

The incidence and frequency of TEAEs will serve as safety endpoint of the study.

TEAEs in the Treatment Period

This will be defined as a TEAE (as defined above) with a start date on or after the date of first study treatment administration and before the Week 8 Visit. It will be identified, if eCRF question 'Did the event occurred:' was answered with 'During Treatment period'.

TEAEs in the Follow-up Period

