This is defined as a TEAE (as defined above) with a start date on or after the Week 8 Visit. It will be identified, if eCRF question 'Did the event occurred:' was answered with 'During Follow-Up period'.

For listing purposes, treatment day of onset of AE will be presented according to the definition given in section 8.1.

Missing Codes or Incomplete AE start dates:

In the event that coding information will not be available for a specific AE, the event will be presented as 'Uncodable Event'). However, for final TLFs it is anticipated that all events are coded.

If the eCRF question 'Did the event occur:' was not answered, AEs will be classified to subclass Non-TEAEs, TEAE in the Treatment Period or TEAE in the Follow-up Period based on the AE onset date utilizing the definitions given above (including those for ocular events in untreated eyes). If this is not possible, the event will be classified as TEAE in the Treatment Period.

Missing and/or incomplete AE onset dates will be imputed for calculating relative start and stop days only. Dates will be listed as missing/incomplete [with "-" replacing missing information] but the onset Day listed between square brackets to denote it was calculated based on missing data (i.e. [1]).

Missing and/or incomplete dates will be imputed in a manner that assumes the worst case scenario:

- For a missing start day (but month and year is available), onset is assumed on the first day of the respective month.
- For a missing start month (but year is available), onset is assumed on 1st January of the respective year.
- For a completely missing start date, no imputation will be performed.

If for Non-TEAEs this procedure results in an onset date before date of informed consent, informed consent date will be used.

If for TEAEs during treatment period this procedure results in an onset date before date of first study treatment, date of first study treatment will be used.

If for TEAEs in the Follow-Up period this procedure results in an onset date before date of Week 8 visit, date of Week 8 visit will be used.

Best Corrected Visual Acuity (BCDVA)

Best-corrected visual acuity is measured at all trial visits using standard charts, lighting, and procedures. All eyes must be tested at 4 meters first, even if the refraction was performed at 1 meter. When a patient cannot read at least 20 letters on the chart at 4 meters, the patient is tested at 1 meter.

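### The Day 52 cut in SAP 8.2.1 counts patients who leave on or after that day without a Week 8 visit as follow-up discontinuations, at odds with the SAP's adverse event periods

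*SAP*

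**What the plan says.** SAP 8.2.1 uses the date on the End of Study page. The rule reads "If the study day of discontinuation/study completion as documented on the eCRF page is below 52 days, discontinuation will be considered as" falling in the treatment period; "otherwise it will be considered as 'During Follow-Up Period". Neither the last-dose date nor attendance at Week 8 enters the rule. SAP 10.1 and Table 14.1-1.2 report the resulting counts, and the primary reasons within each period, by treatment and overall on the Enrolled Set.

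The day count starts at Baseline as Day 0: "Study day 1 is, subsequently defined as the day after the Baseline Visit". Table 2 in SAP 8.1 gives the Week 8 window as "Study day in [52 – 60".

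The Protocol continues dosing beyond Day 52. Section 3.1.3 says for the vehicle arm "One drop of vehicle (40 µL) will be instilled into each eye six times daily, for 56 consecutive days" and gives the same length for rhNGF. Section 6.1 has patients "self-administer at home the subsequent doses from the evening of Day 28±2 to the evening of Day 56±4".

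SAP 8.2.8 places the boundary elsewhere for adverse events. A treatment-period event is one "with a start date on or after the date of first study treatment administration and before the Week 8 Visit"; a follow-up event is one "with a start date on or after the Week 8 Visit". In practice the period is read from an eCRF question. The dates are used when that question is unanswered, and an event that still cannot be placed goes to the treatment period.

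**The concern.** Day 52 is the earliest day on which a Week 8 visit is in window. It does not mark the end of treatment for anyone in particular. Two kinds of patient receive a period label that does not describe them:

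- A patient still on drug who leaves on Day 54 before the Week 8 visit.
- A patient last seen at Week 4 who misses Week 8 and whose loss is recorded on, say, Day 70.

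Both are filed under follow-up, together with their reason for leaving. If the first patient leaves because of an adverse event that began on Day 54, the written definition in 8.2.8 makes the event a treatment-period one, while the discontinuation it caused is tabulated in follow-up.

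At stake is the by-arm count of treatment-period exits and their reasons. With few dropouts expected, one moved patient is visible in that table.

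**Working it through.** **Inputs**

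- Cut at study day 52 (SAP 8.2.1).
- Week 8 at Day 56 ± 4 (SAP 8.1, Table 2).
- 56 days of treatment (Protocol 3.1.3).
- Dosing to the evening of Day 56 ± 4 (Protocol 6.1).
- 5% dropout and 150 patients (SAP 4.6).

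**Step 1: where 52 comes from.** 56 − 4 = 52, the lower limit of the Week 8 window; the upper limit is 56 + 4 = 60.

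**Step 2: the two rules on the same day.** Give each study day from 0 to 84 one label by 8.2.1 (below 52 or not) and one by the dated definition in 8.2.8 (before the Week 8 visit or not).

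| Week 8 visit on day | Days on which the rules disagree | Number of days |
|---|---|---|
| 52 | none | 0 |
| 54 | 52–53 | 2 |
| 56 | 52–55 | 4 |
| 58 | 52–57 | 6 |
| 60 | 52–59 | 8 |
| no visit | 52–84 | 84 − 52 + 1 = 33 |

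Within the window, the rules agree throughout only if the visit falls exactly on Day 52. For a patient with no Week 8 visit they disagree on every day from 52 on. Exits before Day 52 are classed correctly. The one exception is an out-of-window early visit: with Week 8 held on Day 50, an exit on Day 50 or 51 is a treatment-period discontinuation under 8.2.1 but falls in follow-up under 8.2.8.

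**Step 3: expected number of patients.** The dropout assumption gives 0.05 × 150 = 7.5 patients. The number of days on drug that 8.2.1 assigns to follow-up is (last dosing day − 52 + 1).

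| Last dosing day | Days affected | Share of days from Day 0 to last dose | Patients, exits even over dosing days | Patients, exits even over Days 0–84 |
|---|---|---|---|---|
| 55 (56 days from Day 0) | 4 | 4/56 = 7.1% | 7.5 × 4/56 = 0.54 | 7.5 × 4/85 = 0.35 |
| 56 (56 days from Day 1) | 5 | 5/57 = 8.8% | 7.5 × 5/57 = 0.66 | 7.5 × 5/85 = 0.44 |
| 60 (end of window) | 9 | 9/61 = 14.8% | 7.5 × 9/61 = 1.11 | 7.5 × 9/85 = 0.79 |

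The range is 0.35 to 1.11, or about 0.4 to 1.1 patients. The last row is an upper bound, because Protocol 3.2.1 supplies 2 × 28 = 56 daily vials.

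**Step 4: losses recorded late.** Step 3 counts only exits on dosing days. A patient lost after Week 4 whose loss is dated after the missed Week 8 visit would be added to it. Neither document says how such a date is chosen, so no figure is attached.

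**The case against.** The strongest reply is that this is a label in one descriptive table of an exploratory study, and that the affected patients can be found by hand. SAP 10.1 adds first and last intake dates to the discontinuation listing, and protocol deviations are reviewed before unmasking. That stands, and it keeps the point minor. It does not correct the table itself, which gives reasons by period and arm.

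A reader might infer three stronger points. The documents do not support them.

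- *That this table is needed to show how many primary values rest on LOCF.* SAP 9.1 requires missing and non-missing counts, Tables 14.2-2.1 and 14.2-2.2 give observed SANDE scores by visit, and SAP 10.5.1 marks imputed values in the listing. The disposition table is on the Enrolled Set, so it would not give the FAS count under any cut. A patient who leaves on Day 54 may also have a SANDE score from an early termination visit, available to carry forward.
- *That the adverse event tables must contradict the disposition table.* The event period normally comes from the eCRF question, so the conflict is between written definitions and arises in the output only where the answers or the fallback follow them. The safety endpoint is all treatment-emergent events, whatever the split.
- *That a large share of the dropouts is misfiled.* This needs a site dating practice that the documents do not describe.

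It is also tempting to end the adverse event treatment period at the last dose for patients who stop early. That is debatable, and combined with a disposition boundary at Week 8 it would create a new mismatch of the same kind.

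**Conclusion.** The point holds for patients whose recorded exit is on Day 52 or later and who had no Week 8 visit. SAP 8.2.1 puts them, with their primary reason, in follow-up, while the written definition in 8.2.8 splits the periods at the visit itself. For these patients the direction is certain: treatment-period exits are undercounted.

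The size is about 0.4 to 1.1 patients. This assumes the plan's 5% dropout, exits spread evenly over dosing days or over Days 0–84, and a last dosing day between 55 and 60. It would be larger only if losses are dated after the missed visit, which is an assumption. The FAS, the LOCF primary analysis and the sample size do not depend on this label. Severity: minor.

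**What to change.** In SAP 8.2.1, replace the Day 52 cut with Week 8 attendance. A discontinuation is in the treatment period if the patient left without a Week 8 visit, and in follow-up only if the Week 8 visit took place. Disposition and adverse event periods then share one boundary, and the early-visit case in Step 2 is resolved too. It would help to state that the Week 8 visit means the visit recorded as such on the eCRF, in line with SAP 8.1, which analyses visits as collected. SAP 8.2.8 needs no change for this purpose.

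The cost is one sentence in the SAP and a small change in programming, using visit data already collected. The one downside is that the reported treatment-period dropout may look slightly higher.

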8.2.2 Demographic Characteristics

Demographic characteristics are recorded on the eCRF Page "Demography".

Gender (Male, Female), Ethnicity ('Hispanic, Latino, Spanish', 'Not Hispanic, Latino, Spanish'), and Race ('White', 'Black or African American', 'Asian', 'Native Hawaiian or Other Pacific Islander', 'American Indian or Alaska Native', 'Other') will be analyzed as recorded on the eCRF.

Age (years) will be calculated at Baseline as:

- the integer part of $(\text{Date of Baseline Visit} - \text{date of birth})/365.25$.
In case of incomplete dates, missing days will be set to 1st and missing months will be set to July.

8.2.3 History of Dry Eye Disease and other Medical History

The details of History of Dry Eye are recorded on the "Medical history" eCRF page.

The time since initial diagnosis of Dry Eye Disease (months) is calculated as

- $(\text{Date of Baseline Visit} - \text{Date of first diagnosis of Dry Eye Disease}) * 12 / 365.25$

If the date of initial diagnosis is partially missing then the last day of the month, or the 31DEC of the year will be assumed. Date of Baseline Visit is used, if imputed date will be after this date.

Etiology is assessed as wild text and will be listed only.

Identification of study eye ('Right eye', 'Left eye') is recorded on the "Study Eye" eCRF page and will be analyzed as recorded on the eCRF.

All other medical history is recorded on the "Medical history" eCRF page.

Medical history contains information about conditions that a patient might have suffered prior to Baseline visit, or conditions that are ongoing at the time of the Baseline visit.

The medical history terms as specified by the investigator will be coded to a Preferred Term (PT) and a System Organ Class (SOC) using the Medical Dictionary for Regulatory Activities (MedDRA) thesaurus version 19.1.

In the event that coding information will not be available for a specific medical history record, the record will be presented as 'Uncodable Record'). However, for final TLFs it is anticipated that all medical history records are coded.

8.2.4 Prior and Concomitant Medication

Prior and Concomitant medication data will be collected throughout the study on the 'Prior and Concomitant Medications' eCRF page. *All medications (including over-the-counter drugs, herbal products, vitamins, and antacids) taken within 4 weeks prior to the start of and throughout the study must be recorded.*

Prior medications are defined as medications that were stopped before the date of first study treatment administration, i.e. stopped on treatment day 1 or before.

Concomitant medications comprise all medications that a patient used during at any stage during the treatment or Follow-up period, i.e. medications, which are ongoing at treatment day 1 or medications which started on or after treatment day 1.

Relative start and stop day of a medication will be defined as the corresponding treatment day as specified in section 8.1. If for a medication 'Ongoing' duration is specified, no stop day will be calculated.

From the above follows that a medication can either be prior or concomitant.

The Investigator Terms (Generic Medication Name, and Indication) will be coded using the Enhanced WHO-Drug Dictionary, Version MARCH/2016.

Prior and concomitant medication data will be summarized by WHO-ATC class 2 (Therapeutic Main Class) and WHO drug name (Preferred Term).

Missing Codes or Medication Dates Imputation:

In the event that coding information will not be available for a specific concomitant medication, the concomitant medications will be presented as 'Uncodable Medication'. However, for final TLFs it is anticipated that all medication records are coded.

Missing and/or incomplete dates for prior and concomitant medications will be imputed for calculating relative start and stop days only. Dates will be listed as missing/incomplete [with "-" replacing missing information] but the Start/Stop Day listed between square brackets to denote it was calculated based on missing data (i.e. [-28], [1], [Ongoing]).

Missing and/or incomplete dates will be imputed in a manner that assumes the worst case scenario.

Technically, incomplete stop dates will be imputed as follows:

- For a missing day (but month and year is available), it will be assumed that medication have been stopped on the last day of the respective month.

- For a missing month (but year is available), it will be assumed that medication have stopped on 31st December of the respective year.
- For a completely missing stop date, the medication will be assumed as being ongoing.

Similarly, incomplete start dates will be imputed as follows:

- For a missing start day (but month and year is available), onset is assumed on the first day of the respective month.
- For a missing start month (but year is available), onset is assumed on 1st January of the respective year.
- For a completely missing start date, no imputation is performed. However, the medication will be considered as concomitant, unless indicated different by stop date.

8.2.5 Measurements of Exposure and Treatment Compliance

Exposure

Exposure will be summarized by the parameters Treated Eyes and Treatment Duration.

Information about the type of eyes treated are recorded on the eCRF page 'Study Eye' at the Baseline Visit. Generally, both eyes should be treated. However, there might be circumstances, where only one eye is treated. For the analysis, the parameter Treated Eyes will be presented in the following categories:

- Both eyes: answer to eCRF question 'Which eye(s) will be treated' is Right Eye and Left Eye.
- Study eye only: only one eye is ticked for eCRF question 'Which eye(s) will be treated', which coincides with the study eye as specified in the eCRF question 'Which is the study eye?'.
.
- Non-Study eye only: only one eye is ticked for eCRF question 'Which eye(s) will be treated', which does not coincides with the study eye as specified in the eCRF question 'Which is the study eye?'. However, this situation is not expected for the study, as this might reflect a protocol deviation.

Treatment duration will be derived based on dates of first and last study treatment administration recorded on the 'Study Drug Dosing Dates' eCRF page. It will be calculated as

- Date of Last Study Treatment Administration – Date of First Study Treatment Administration +1. If a patient has not received any study treatment in any eye, treatment duration will be set to 0.

Compliance

The assessment of patients' compliance to the IMP will be made by determining the number of study medication vials dispensed to the patient at Day 0 baseline Visit, Week 4 Visit and the number of unused study medication vials returned at Week 4 Visit and Week 8 Visit, respectively. This information is collected on eCRF page 'Study Drug Dosing and Accountability'.

Compliance will be evaluated according to the following formula:

$$\text{Compliance (\%)} = 100 * \frac{\text{Number of vials dispensed} - \text{Number of unused vials returned}}{\text{Number of expected days on treatment}}$$

The number of expected days on treatment will be set to 56. For each patient, the number of vials dispensed will be derived as the sum of provided numbers in the column “# Vials Dispensed” on the eCRF Page ‘Study Drug Dosing and Accountability; the number of unused vials returned will be derived as the sum of provided numbers in the column “# Vials Unused” on the eCRF Page ‘Study Drug Dosing and Accountability.

Compliance will be presented categorical as <80%, 80-120%, >120%.

No further analyses will be planned on compliance. All other collected data including diary information on treatment compliance will be evaluated during the BDRM for relevant protocol deviations and will be listed.

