10.3 Compliance with IMP administration

The assessment of patients' compliance to the IMP will be made by determining the number of study medication vials dispensed to the patient at Day 0 baseline Visit, Week 4 Visit and the number of unused study medication vials returned at Week 4 Visit and Week 8 Visit, respectively. Compliance will be evaluated according to the following formula:

$$\text{Compliance} = \frac{\text{Number of vials dispensed} - \text{Number of unused vials returned}}{\text{Number of expected days on treatment}}$$

Gross non compliance will be defined as compliance lower than 80% or greater than 120% and in case of gross non compliance the patient will be excluded from the Per Protocol Set (see § 10.1.3). Since this definition does not warrant that the study eye treatment is compliant, if indicated the SAP will contain further definitions based upon the diary card information.

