7.1 Analysis Sets

A patient will be defined as *screened* after the signature of the informed consent, regardless of the completion of all the screening procedures. A patient will be defined as screen failure, if he was screened but not enrolled in the study.

Enrolled Set:

A patient will be defined as *enrolled* in the study if he/she is randomized. This analysis set will be used for demographic, baseline and background characteristics.

If not stated otherwise, analyses based on the Enrolled Set will be summarized by the treatment randomized.

Safety Set (SAF):

The Safety Set will be defined as all enrolled patients who receive at least one dose of the investigational medicinal product (IMP). *This analysis set will be used for the safety analysis.* All analyses based on the SAF will be summarized by the treatment received.

Full Analysis Set (FAS):

The Full analysis set will be defined as all patients in the SAF, who have receive at least one dose of the IMP in the study eye and who have at least one post-baseline Sande score assessment or another post-baseline efficacy measurement in the study eye. This analysis set will be used for efficacy analyses. All efficacy analyses based on the FAS will be summarized by the treatment randomized.

Per Protocol Set (PPS):

The Per Protocol set will be defined as *all patients in the FAS who fulfill the study protocol requirements in terms of investigational medicinal product intake and collection of primary efficacy data and with no major deviations that may affect study results. This analysis set will be used for supportive efficacy analysis.* All efficacy analysis based on the PPS will be summarized by the treatment randomized.

After all patients have completed study and prior to database lock, a blinded data review meeting (BDRM) will be performed to assign patients to analysis sets. Details of BDRM will be specified in a separate BDRM-plan.

The BDRM plan will consider the following criteria for exclusion of a patient from the PPS:

- *lack of compliance with investigational medical product administration*

A compliance below 80% or greater than 120% will lead to exclusion from the PPS (compliance definition please refer to section 8.2.5).

- *exposure to an IMP dose different from the one assigned to the patient*

- *missing primary efficacy data*
- *failure to satisfy any inclusion/exclusion criteria (eligibility violations)*
- *intake of prohibited medications*

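### The vial-count compliance score treats unreturned vials and instillations missed within a day as taken, and neither document gives a diary criterion to catch them

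*SAP*

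**What the plan says.** Protocol 10.3 takes the vials dispensed at Day 0 and Week 4, subtracts the unused vials returned at Weeks 4 and 8, and divides by the expected days on treatment. The cut is stated there: "Gross non compliance will be defined as compliance lower than 80% or greater than 120"%. SAP 8.2.5 keeps the formula, fixes the denominator ("The number of expected days on treatment will be set to 56") and defines the subtracted term: "the number of unused vials returned will be derived as the sum of provided numbers in the column" that records unused vials. SAP 7.1 makes the cut binding: "A compliance below 80% or greater than 120% will lead to exclusion from the PPS".

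On the diary, Protocol 10.3 admits that the vial count does not guarantee compliance in the study eye and adds that "if indicated the SAP will contain further definitions based upon the diary card information". SAP 4.7 replies that the diary card is not eye-specific, so it sets no such definitions. SAP 8.2.5 then says "No further analyses will be planned on compliance", but also that "diary information on treatment compliance will be evaluated during the BDRM for relevant protocol deviations". On that blinded data review meeting (BDRM), SAP 7.1 says "Details of BDRM will be specified in a separate BDRM-plan". SAP 10.2 excludes any patient with a major deviation from the PPS.

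SAP 10.4 tabulates the vial score in three bands (<80%, 80-120%, >120%) and lists the diary information.

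**The concern.** The score subtracts only what the patient brings back as unused. A vial that is lost or left at home is therefore credited as a day of treatment. Protocol 3.2.2 supplies one vial for all six daily administrations to both eyes, so opening it earns a full day however many drops were given.

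The return route is also incomplete. Medication compliance is checked at Weeks 4 and 8 only (schedule of procedures), and neither the early termination visit (Protocol 6.1) nor the discontinuation procedures (Protocol 13.4.2) list a vial return. A patient who stops after the Week 4 dispensing has no listed step that brings the second box into the count.

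At stake is the plan's own check on protocol deviations. SAP 10.5.1 repeats the primary analysis on the PPS for that purpose. If under-dosed patients score 100%, the vial criterion cannot remove them, and the compliance table reports them as adherent.

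**Working it through.** **Inputs**
- Two monthly boxes of 28 vials each (Protocol 3.2.1).
- One vial per day, six instillations per eye (Protocol 3.2.2).
- Score = 100 × (dispensed − unused returned) / 56, with limits of 80% and 120% (SAP 8.2.5 and 7.1).

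**The plan's own figure.** 2 × 28 = 56 vials at one per day gives 56 days, which matches the denominator. Scheduled instillations per eye are 6 × 56 = 336.

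**Pass mark.** 0.8 × 56 = 44.8, so 45 credited vials are needed. Returning 11 unused gives 45/56 = 80.4% (pass); returning 12 gives 44/56 = 78.6% (fail). With the planned supply the score cannot exceed 56/56 = 100%. The upper limit needs more than 1.2 × 56 = 67.2 vials, so only the lower limit operates.

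**Patterns that pass with 56 vials dispensed** (illustrative; the documents give no rates of vial loss or missed drops)

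| Pattern | Unused returned | Score | Actually taken |
|---|---|---|---|
| Box 1 used, box 2 not returned | 0 | 56/56 = 100% | 28/56 = 50.0% supported |
| 40 used, 5 of 16 unused kept at home | 11 | 45/56 = 80.4% | 40/56 = 71.4% |
| 35 used, 10 of 21 unused kept at home | 11 | 80.4% | 35/56 = 62.5% |
| 28 used, 17 of 28 unused kept at home | 11 | 80.4% | 28/56 = 50.0% |
| All vials opened, 4 of 6 daily | 0 | 100% | 224/336 = 66.7% |
| All vials opened, 3 of 6 daily | 0 | 100% | 168/336 = 50.0% |
| 45 vials opened, 4 of 6 daily | 11 | 80.4% | 180/336 = 53.6% |

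In general, a patient who used u < 45 vials passes once 45 − u unused vials stay at home. Giving 5 of 6 daily (280/336 = 83.3%) passes on either measure, so within-day misses matter only from two per day upwards when every vial is opened.

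**Role of the 56.** It causes none of these results. A patient who stops before the Week 4 dispensing holds only 28 vials, scores at most 28/56 = 50.0% and is excluded. A fully adherent patient who returns everything scores 44/56 = 78.6% on stopping at day 44 and 45/56 = 80.4% at day 45.

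**Check of the remedy.** SAP 8.2.5 already derives treatment duration from the first and last dosing dates. If used vials are capped at that duration, a day-35 stop with box 2 unreturned falls from 56/56 = 100% to 35/56 = 62.5%. The cap does nothing for a patient whose last dose is near Day 56; there a dose count is needed. An 80% cut on instillations is 0.8 × 336 = 268.8. If the first day holds only one instillation, it is 0.8 × (55 × 6 + 1) = 0.8 × 331 = 264.8. A partial first day therefore hardly moves the cut.

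**The case against.** The vial score is not the only gate. Site staff assess compliance at Weeks 4 and 8 from the diary as well as the returned boxes (Protocol 6.1). The masked BDRM evaluates diary data, a major deviation removes a patient from the PPS, and the PPS definition itself requires that the intake requirements be met. The BDRM plan is a separate document, not available here, and may hold a numeric diary rule. All of this stands. A reader might infer that under-dosed patients will necessarily enter the PPS, and the documents do not support that. What remains is that neither document states a diary criterion, and that the table would show these patients as 80-120% whatever the BDRM decides.

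The unreturned-box example is open to challenge. The box is due back at Week 8 and the site must keep records of use or loss (Protocol 3.3). A patient who misses Week 8 might also be excluded for lacking primary efficacy data; the SAP does not say whether a carried-forward value counts. The within-day example does not depend on any of this.

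A reader might also infer that the SAP ignored a protocol commitment on diary definitions. It did not: the provision was conditional and concerned the study eye, and SAP 4.7 answers it openly. That answer does not, however, rule out counting administrations, because patients are told to enter the time of self-administration (Protocol 6.1).

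Finally, the set is supportive and the study exploratory. That limits the importance of the point but does not make the score correct.

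**Conclusion.** The point holds in a limited form. As written, the score credits unreturned vials and missed within-day instillations as taken, so it can show 100% where 50% was taken or can be supported, and 80.4% where 53.6% was taken. Such patients pass the only numeric compliance criterion for the PPS in these documents; a BDRM exclusion remains possible on unstated grounds.

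The effect is confined to the compliance table and the supportive PPS analyses. A reader might infer a bias in the primary result. There is none from this source, because the primary analysis uses the FAS and applies no compliance cut.

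Two things cannot be settled from the documents: how many patients would be affected, and how sites complete the unused-vial column for vials not brought back. The calculation takes the SAP wording literally, so that only returned vials are subtracted. The point is worth correcting before unmasking.

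**What to change.** Before unmasking:

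1. In SAP 8.2.5, count as used no more vials than the treatment duration already derived there. State that vials returned at any visit, including early termination, enter the count. Flag a dispensed box with no return entry as unaccounted, not as used, and refer it to the masked BDRM for a decision against the last-dose date and the diary.
2. Add a supplementary measure: diary-recorded administrations divided by instillations scheduled between first and last dose, allowing for partial first and last days. Count unrecorded administrations as missed, and show wholly missing diaries separately as unknown. Leaving blanks out of both numerator and denominator would give 100% by construction. Report the measure beside the vial score. Apply it with the existing 80% cut, in addition to the current criteria, to form a sensitivity PPS. It should not replace the vial score, because its denominator ends at the last dose and so ignores early stopping.

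The cost is SAP and BDRM-plan wording plus programming, with no new visits or assessments. Dosing dates are on the eCRF and diary entries are already to be listed. It is assumed that the eCRF holds individual administration times; its fields are not shown. Diary data are self-reported and may be incomplete. Step 1 will not detect a few vials kept back from a box that was otherwise returned when dosing ran to Day 56; only the diary measure can show those.
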